In a case report by Baker and Wilson²³ examining Astym in the treatment of a bilateral carpal tunnel syndrome (CTS) patient, they found that Astym was shown to be an effective treatment approach for resolving the patient's symptoms. An article by Ettema et al²⁷ reported on the physiological changes that occur in the subsynovial layer of tissue during carpal tunnel. An electron microscope found fibrotic changes as a result of a shearing injury. The anatomy of the flexor tendons are similar to that of the tendons involved in de Quervain's. If Astym has been shown to be an effective treatment approach for

CTS, then it is reasonable to hypothesize that Astym would be an effective treatment for de Quervain's tenosynovitis. But does the Astym treatment along with stretching and exercise work better than the gold standard of care of splinting and exercise alone.

- **Study design:**

The research question for this study is:

Does adding an Astym treatment protocol to existing standard of care treatment of de Quervain's tenosynovitis increase outcomes of individuals with this condition?

The Alternative Hypothesis for this study is:

Participants receiving the Astym treatment protocol will have greater improvements in pain reduction and function as compared to those subjects in the control group receiving the standard of care therapy treatment

This is a randomized controlled study using repeated measure design with 2 groups:

- A. Control group who will receive standard of care rehabilitation intervention for the treatment of de Quervain's tenosynovitis.
- B. Experimental group will receive standard of care rehabilitation interventions plus Astym treatment protocol.

Three outcomes measures will be used for the study:

1. **Numeric Rating Scale for Pain**- This scale is a single point scale from 0-10. The participant picks one number to represent their pain, where 0 represents no pain and 10 represents worst pain imaginable.
2. **Quick Dash**-This is an 11 item questionnaire in which participants self-score themselves using a 1-5 point scale. One represents no difficulty in performing task whereas 5 represents unable to perform task.
3. **Sequential Occupational Dexterity Assessment**-This is a test to measure dexterity and bimanual abilities in activities of daily living. It includes 12 tasks with participants being scored on their ability, difficulty and pain during the task.

II. Characteristics of research population

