Patients with the diagnosis of de Quervain's from referring physician will be provided with a pre-fabricated Ossur thumb spica splint for use as indicated in splinting program^{13,15-17}, instructed on a home exercise program as part of standard of care along with being educated about the research study. If interested, they will be consented, and scheduled for a follow-up visit 3 weeks later. If not interested, they will be scheduled for a 3 week follow-up session and treated if needed. Upon their return, the patients will be screened by the researcher OT for inclusion and exclusion criteria. If subject meets the criteria, they will be randomized into either (1) control or (2) Astym group and then evaluated by a blinded Certified Hand Therapist or hand therapist. Fine motor coordination will be tested by using the Sequential Occupational Dexterity Assessment (SODA)³⁹. Pain and functional loss will be measured via the Visual Analog Scale (VAS)⁴⁰ and Quick Dash⁴¹⁻⁴⁵. They are then seen for formal therapy 2/x for 6 weeks for a total of 12 therapy session. If the subject does not meet criteria or decide not to participate in

the study, they are deemed a screen failure, dismissed from study, and will continue with treatment if needed.

The subjects will be seen twice a week for 6 weeks for 30 minute sessions by a separate treating therapist from the evaluating therapist. The patient will start at phase I; however, will not progress to the next phase of treatment if symptoms and pain are provoked.. When he/she tolerates exercises without pain or exacerbation of symptoms, the patient is progressed to Phase II and then phase III .Prior to discharge, if the subject has not achieved phase III, the therapist will incorporate Phase III exercises, for strengthening and functional movements of the hand, forearm, elbow and shoulder to be completed at home. . All subjects, either in control or Astym group, will receive only 12 sessions of therapy regardless if they progress through the all 3 phases. Astym group will receive traditional therapy with Astym every session, while the control group will only receive traditional therapy. See protocol below.

Control group: Traditional therapy for de Quervain's Tenosynovitis^{17-19, 21-22, 30-33:}

Phase I: Reduction of splint use andstrengthening initiated once patient can perform pain free AROM (monitor symptoms to not exacerbate condition)

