- Thumb abduction and extension with yellow power web or light resistance rubber bands 3 sets of 10 reps
- Continue stretching 4x/day for 30-45 seconds, with stretching prior to and after exercises:
 - UD of wrist with thumb tucked under fingers and wrist in neutral
 - Wrist flexion with elbow extended forearm pronated
 - Wrist extension with elbow extended forearm supinated

Phase III: Continue therapy, incorporate strengthening and functional movements for forearm, elbow and shoulder and prepare patient for discharge to home exercise program

- Goals include: Pain free functional use of affected extremity during all tasks without use of splint
- Replace moist heat pack with Upper Body Ergometer for 10 min
- **Continue Astym to affected extremity per de Quervain's protocol, including de Quervain's strokes for a max of 12 sessions**
- Continue stretching 4x/day for 30-45 seconds, with stretching prior to and after exercises:
 - UD of wrist with thumb tucked under fingers and wrist in neutral
 - Wrist flexion with elbow extended forearm pronated
 - Wrist extension with elbow extended forearm supinated
- Adding multi joint strengthening exercises to match job demands using dumbbells
- Patient discharged to HEP after 12 sessions of therapy with review of ergonomics, stretches, and exercises at last session.

Three months after discharge from CMC, Quick DASH and VAS scale scores and questionnaire regarding patient compliance will be completed by phone interview.

Data Analysis and Monitoring

Descriptive statistics will be used along with inferential statistics. The alternative hypothesis will be addressed using a mixed design analysis of variance to test for differences between-groups and within-groups. In addition we will also analyze the interaction effect between study group and time. All analyses will have an alpha of 0.05. Malchy's test for sphericity will be performed along with a Bonferroni comparison. If Malchy's test for sphericity is significant then a Greenhouse-Geisser or Huynh-Feldt correction will be used. In addition a repeated measure MANOVA may be used to test the dependent variables in a multivariate method if in fact the dependent variables demonstrate a relationship of linearity.

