Based upon the planned analyses for the primary hypothesis, a mixed repeated measure design with 1 between factor (group membership) and 1 within factor (repeated measures) has 2 groups with 16 subjects each for a total of 32 subjects. This design achieves a 80% power to test the between factor using the above mentioned mixed methods ANOVA using a 5% significance level with an actual Cohen's F effect size of .398

Data Storage and Confidentiality

All written data will be stored in a locked draw of a locked office. For data analysis purposes all data will also be stored using Microsoft Excel/ReCap Software. To ensure confidentiality all participants will be categorized alphanumerically.

IV. Risk/Benefit Assessment

- Risk

Potential side effects of Astym treatment include:

- 1) Ecchymosis to the treatment area, typically where fibrotic tissue and healing is indicated.
- 2) Increased pain or soreness for 24-48 hrs after treatment.
- 3) Increased inflammation of affected extremity after treatment.
- 4) Vagal response during treatment due to neural effect on tissue from the Astym treatment that include but are not limited to light headedness, feeling faint and nausea.

- Protection against risks

Patient education of these risks will help the patient understand some of the temporary side effects that they may experience. Icing 3-4 hrs after treatment can limit some of the side effects and help with pain and inflammation. Eating 1 hour prior to treatment will also limit vagal response during the Astym treatment. Prior to therapy, the patients will be encouraged to tell their therapist to stop treatment if they do not wish to continue if they are experiencing any of these symptoms and/or do not wish to continue in the study.

- Potential benefits to subjects:

Patients will receive Astym treatment to the affected extremity in addition to traditional therapy they would normally receive when being treated for de Quervain's tenosynovitis. Astym treatment will be delivered by a qualified, specially trained occupational therapist where instruments will be applied topically to the skin with moderate pressure to stimulate a healing and regenerative response. . We believe the additional Astym protocol will increase functional levels for patients along with a greater social benefit of the knowledge gained from this experimental study.

- Subject Compensation:

There will be no compensation to patients for this study.

V. Investigators Qualifications & Experience

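### The hypothesis that Astym gives greater improvement is assigned to the between-groups and within-groups effects of a mixed ANOVA, neither of which fits it; the group-by-time contrast is not named as the deciding test

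*Combined protocol and SAP*

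**What the plan says.** Section I, Study design, states a comparative hypothesis: the Astym participants "will have greater improvements in pain reduction and function as compared to those subjects in the control group receiving the standard of care therapy treatment".

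Section III, Data Analysis and Monitoring, assigns the test: "The alternative hypothesis will be addressed using a mixed design analysis of variance to test for differences between-groups and within-groups". The next sentence reads "In addition we will also analyze the interaction effect between study group and time", and then "All analyses will have an alpha of 0.05". The second paragraph of that section ties the primary hypothesis to a sample size of 16 per group: "This design achieves a 80% power to test the between factor", with a Cohen's f "effect size of .398".

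Both arms are actively treated. Section III, Research design: "Astym group will receive traditional therapy with Astym every session, while the control group will only receive traditional therapy". All three outcomes are measured at baseline and discharge. Pain and Quick DASH are measured again at 3 months, and SODA is not.

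**The concern.** A mixed ANOVA with arm and visit has three effects, and they answer different questions.

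- **Within-groups (time).** The null is that mean scores do not change over visits. Arm does not enter it.
- **Between-groups (arm).** The null is that the arms have the same mean score averaged over all visits, including the baseline taken before treatment.
- **Group-by-time interaction.** The null is that the arms change equally. This is the one that expresses greater improvement.

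The sentence that assigns the hypothesis names the first two. Reading within-groups as before/after tests inside each arm does not help, because change in the Astym arm also contains standard care, natural course and regression to the mean.

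At stake is what the trial can conclude. Without a deciding effect, a time result that is silent on Astym sits beside the hypothesis with the same alpha as the result that answers it. The effect that carries the power statement is diluted by baseline.

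**Working it through.** **Inputs from the documents.** N = 32 (16 per arm); alpha 0.05; f = 0.398, which for two groups is d = 2 × 0.398 = 0.796 SD; two visits for SODA, three for pain and Quick DASH.

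**Not in the documents, so assumed.** Correlation between visits ρ = 0.3 to 0.7, equal for all pairs; a shared improvement δ of 0.3, 0.5 or 0.8 SD in both arms.

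**1. The plan's own power figure.** For the between factor with m visits, λ = f²Nm / (1 + (m−1)ρ) on 1 and 30 df, where f²N = 0.398² × 32 = 5.069.

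- One measurement: λ = 5.069, power 58.7%.
- m = 2, ρ = 0.2: λ = 5.069 × 2 / 1.2 = 8.45, power 80.3%.
- m = 3, ρ = 0.4: λ = 5.069 × 3 / 1.8 = 8.45, power 80.3%.
- ρ = 0.5: 71.1% (m = 2) or 76.1% (m = 3).

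The stated 80% is reachable, but only with a correlation and number of visits that the plan does not give. It is also power for a difference in the average over visits.

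**2. Time test when Astym adds nothing.** For two visits, λ = Nδ² / (2(1−ρ)) on 1 and 30 df. Example: δ = 0.5, ρ = 0.5 gives 32 × 0.25 / 1 = 8.0 and a 78% chance of significance.

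| Shared improvement | ρ = 0.3 | ρ = 0.5 | ρ = 0.7 | Interaction |
|---|---|---|---|---|
| 0 | 5% | 5% | 5% | 5% |
| 0.3 SD | 28% | 38% | 56% | 5% |
| 0.5 SD | 64% | 78% | 94% | 5% |
| 0.8 SD | 96% | 99% | >99% | 5% |

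For three visits, with the improvement reached at discharge and held, λ = (2/3)Nδ² / (1−ρ) on 2 and 60 df. This gives 28–59% at 0.3 SD and 67–97% at 0.5 SD; simulation gave 66–96% at 0.5 SD, the same within simulation error. Over both designs the range is about 64–96% at 0.5 SD.

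**3. Before/after test inside the Astym arm, no Astym effect, 0.5 SD.** An unadjusted paired t-test is significant in 36–67% of trials. With Bonferroni adjustment over three visit pairs, closer to the comparison the plan mentions, it is 20–48%.

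**4. Power if Astym works.** Take equal baselines and D = 0.796 SD at discharge, two visits, n = 16 per arm, 1 and 30 df.

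- Between-groups main effect: the difference in the two-visit mean is D/2, so λ = (D/2)² / [((1+ρ)/2)(2/n)]. At ρ = 0.5: 0.1584 / 0.09375 = 1.69, power 24%.
- Interaction: λ = D² / [2(1−ρ)(2/n)]. At ρ = 0.5: 0.6336 / 0.125 = 5.07, power 59%.

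| ρ | Between-groups | Interaction |
|---|---|---|
| 0.3 | 27% | 45% |
| 0.5 | 24% | 59% |
| 0.7 | 22% | 80% |

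With three visits and the difference held to 3 months, the gap is smaller: 43% against 62% at ρ = 0.5. At ρ = 0.3 it reverses, 51% against 47%, because the interaction then spends 2 df.

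**The case against.** The strongest defence is that the plan lists the standard output of a mixed ANOVA. The interaction is there, at the same alpha, and the opening words of its sentence may be a list connector and not a ranking. The hypothesis is worded comparatively, so a time effect could not satisfy it. The power paragraph points to the between factor, which does involve arm.

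Much of this stands. A reader might infer that the plan will treat a significant time effect as proof that Astym works, or that the trial's false-positive rate is 64–96%. The documents support neither. No sentence says a time effect counts as support, and a significant time test is a correct finding of change over time; it becomes an error only if read as an Astym effect. Nor does the plan omit the right test.

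The size of the time-test figures is also conditional. The documents give no SD, expected change or correlation. At ρ = 0.5 the two-visit rate passes one half only at about 0.4 SD of shared improvement (59%).

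What the defence does not answer is the assignment itself. The hypothesis is tied to two effects that do not measure greater improvement, the one that does is not made decisive, and the power paragraph compounds this by choosing the effect that includes baseline.

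**Conclusion.** The point holds as a poor choice of deciding test. The time effect carries no information on what Astym adds, whatever its p-value. That part is logic and needs no assumption. How often it would be significant without an Astym effect depends on the assumed shared improvement and correlation: about 28–59% at 0.3 SD, about 64–96% at 0.5 SD, and 96% or more at 0.8 SD.

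The between-groups main effect is a valid comparison of arms but a weak one for this hypothesis: 24% power against 59% for the interaction at 0.796 SD, two visits and ρ = 0.5. The disadvantage is clear for two visits across ρ = 0.3 to 0.7. For three visits it depends on ρ.

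The matter should be settled before analysis. It is not evidence that the sponsor intends to claim benefit from change over time.

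**What to change.** Keep the mixed ANOVA and add to Data Analysis and Monitoring:

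> The alternative hypothesis is decided by the between-arm difference in change from baseline to discharge (the group-by-time contrast), reported with its 95% confidence interval. The corresponding contrast at 3 months, for pain and Quick DASH, is secondary. The time main effect and within-arm changes are reported descriptively and are not used as evidence for Astym.

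Naming discharge gives a single contrast that all three outcomes share, and avoids a 2-df interaction for two of them.

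The power paragraph should then be restated for that contrast with its assumed correlation. At 0.796 SD and 16 per arm, power is about 45%, 59% and 80% at correlations of 0.3, 0.5 and 0.7.

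Cost: a wording change and a revised power statement, with no added patients, visits or data. The price is candour. The stated power becomes less favourable unless the correlation is high, and improvement within the Astym arm can no longer be cited as support for Astym.

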- **Number of subjects:** N=32 (16 in each group)
- **Gender of subjects:** Both male and female participants will be included in the study. Demographic data will be included in the analysis of results.
- **Age of subjects:** 18-65yrs old
- **Racial and ethnic origin:** There will be no racial or ethnic restrictions to this study. Data on racial/ethnic origin will not be gathered by the researchers. It is assumed based on current client population that the sample will be diverse.
- **Inclusion criteria:**
 - i. Positive Finkelstein's test: The client will report pain over the first compartment of the extensor retinaculum when the thumb is tucked in the hand and deviated ulnarily.
 - ii. Persistent symptoms for >3 wks which have not resolved after an additional 3 weeks of splinting
 - iii. A diagnosis by a physician of "de Quervain's", "fist compartment tenosynovitis", or "radial styloid tenosynovitis"
 - iv. Patients must agree and comply to a predetermined splinting regimen
- **Exclusion criteria:**
 - i. History of cortical steroid injection to affected wrist and/or thumb
 - ii. Comorbidity such as osteoarthritis, rheumatoid arthritis, auto-immune disease or inflammatory conditions.
 - iii. Clotting deficits
 - iv. Positive Cozen's sign which would indicate intersection syndrome³⁸
 - v. Post-partum mothers <6 months and pregnant women¹⁰⁻¹¹
 - vi. Cleared c-spine via Spurling's Test³⁴⁻³⁵ performed by combining cervical extension, side-bending, and axial compression to the cervical spine.
- **Vulnerable subjects:**
No vulnerable subjects will be included in this study

III. Methods and Procedures:

- **Methods and procedures:**
 - i. Randomized selection of 2 groups both seen for one evaluation and 12 therapy sessions scheduled 2x/week for 6 weeks (total of 12 sessions) for either traditional therapy including splinting and exercises or traditional therapy with Astym protocol. At least 2 days in between therapy sessions to allow sufficient healing.
 - ii. Randomization using computer-generated random numbers. The 3 Outcome measurements will be taken during evaluation and re-evaluation will be collected by two designated hand therapists other than the treating therapist. The data collectors will be blinded.

- iii. Data collection are taken at baseline, and after 12 sessions of therapy at discharge. . Quick DASH and VAS scale scores and questionnaire regarding patient compliance will be completed by phone interview at 3 month follow up.

Research design:

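### The powered group main effect averages in the pre-treatment visit; the group-by-time test that matches the hypothesis has no stated power and does not adjust for baseline

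*Combined protocol and SAP*

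**What the plan says.** The alternative hypothesis (section I, Study design) is that Astym patients "will have greater improvements in pain reduction and function as compared to those subjects in the control group". This is a statement about change.

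The Data Analysis and Monitoring section addresses it with "a mixed design analysis of variance to test for differences between-groups and within-groups", and then adds: "In addition we will also analyze the interaction effect between study group and time". No covariate is named. If the "test for sphericity is significant then a Greenhouse-Geisser or Huynh-Feldt correction will be used".

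The sample-size paragraph has 16 patients per group, a 5% level and Cohen's f of 0.398, and concludes: "This design achieves a 80% power to test the between factor". It gives neither the number of repeated measures nor the correlation between them, and no power for the interaction.

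On timing, Methods and Procedures item iii says: "Data collection are taken at baseline, and after 12 sessions of therapy at discharge". It adds that "Quick DASH and VAS scale scores and questionnaire regarding patient compliance will be completed by phone interview at 3 month follow up". SODA therefore has two visits; pain and Quick DASH have three. Under Research design, eligible patients are evaluated before formal therapy starts, and "they will be randomized into either (1) control or (2) Astym group and then evaluated by a blinded Certified Hand Therapist".

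**The concern.** A group main effect in a mixed ANOVA compares the arms on the average of all visits in the time factor. If one of those visits precedes treatment, randomisation makes the expected difference there zero, and averaging it in shrinks the estimated effect.

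For SODA this cannot be avoided, because there are only two visits and one is baseline. For pain and Quick DASH the plan does not list the levels of the time factor. The sphericity step points to three: with two levels sphericity holds automatically, and the third available visit is baseline.

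Two things are at stake. First, the 32-patient sample size is tied to a quantity other than the one in the hypothesis, and the power of that test falls as the correlation between visits rises. Second, the test that does match the hypothesis leaves precision unused, because it subtracts baseline instead of adjusting for it.

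A smaller, conditional point: if the 3-month call is a level of the time factor and the ANOVA uses complete cases, a missed call also removes that patient's discharge value. The documents give no loss rate.

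**Working it through.** **Inputs from the plan.** n = 16 per arm, N = 32, alpha 0.05 (taken as two-sided, since an ANOVA F test has no direction), f = 0.398. With two equal groups d = 2f = 0.796 SD.

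**Assumptions not in the plan.** Correlation rho of 0.3, 0.5 or 0.7, the same between every pair of visits; equal SDs; no dropout; no expected difference at baseline; the same difference D at discharge and 3 months. T is the number of visits.

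**1. The plan's 80%.** For one measurement the noncentrality is lambda = f²N = 0.398² × 32 = 5.07, with 1 and 30 df, giving 58.7%. With repeated measures, lambda = f²NT/(1 + (T−1)rho).
- T = 3, rho = 0.4: 5.07 × 3/1.8 = 8.45, power 80.3%.
- T = 2, rho = 0.2: 5.07 × 2/1.2 = 8.45, power 80.3%.

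So 80% is reached at rho of about 0.41 (T = 3) or 0.21 (T = 2), provided the full 0.796 SD is present in the average over all visits. With no difference at baseline, the post-treatment difference must then be 0.796 × 3/2 = 1.19 SD or 0.796 × 2 = 1.59 SD.

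**2. Formulas.** For 1-df tests, lambda = effect²/(2 × variance/16).
- Main effect: effect D(T−1)/T, variance (1 + (T−1)rho)/T, 30 df.
- Group by time: lambda = (16/2) × SS/(1−rho), with SS = 2D²/3 (T = 3) or D²/2 (T = 2); df T−1 and 30(T−1).
- ANCOVA at discharge: variance 1−rho², 29 df.
- Raw change to the average of the two later visits: variance (1+rho)/2 + 1 − 2rho, 30 df.
- The same average adjusted for baseline: variance (1+rho)/2 − rho², 29 df.

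Example with T = 3, rho = 0.5, D = 0.796:
- Main effect: 0.531²/(0.667 × 0.125) = 3.38, power 43%.
- Interaction: 8 × 0.4224/0.5 = 6.76 on 2 and 60 df, power 62%.
- Raw average change: 0.6336/(0.75 × 0.125) = 6.76, power 71%.
- Adjusted average: 0.6336/(0.50 × 0.125) = 10.14, power 87%.

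**3. Reading 1: f means 0.796 SD after treatment.** Power at rho 0.3/0.5/0.7:

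| Test | Two visits | Three visits |
|---|---|---|
| Group main effect | 27/24/22% | 51/43/37% |
| Group by time | 45/59/80% | 47/62/84% |
| Raw change to post-visit average | – | 57/71/90% |
| Baseline-adjusted post-visit average | – | 83/87/95% |
| Discharge ANCOVA | 63/71/86% | 63/71/86% |

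With three visits, part of the gain over the 2-df interaction comes from focusing the contrast. The covariate's own share is the step from 57/71/90% to 83/87/95%.

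**4. Reading 2: f means the visit-averaged effect.** D is 1.19 SD with three visits and 1.59 SD with two.

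| Test | Two visits | Three visits |
|---|---|---|
| Group main effect | 77/71/66% | 85/76/68% |
| Group by time | 96/99/100% | 83/94/99.5% |
| Discharge ANCOVA | 99.5/100/100% | 93/96.5/99.5% |

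**5. Precision, independent of f.** With two visits the interaction is exactly a t-test on change. Its variance 2(1−rho) is 2/(1+rho) times the ANCOVA variance 1−rho²: 1.54/1.33/1.18. The 95% CI half-width is t × sqrt(2 × variance/16), with the adjusted variance multiplied by 1 + 1/28 for chance baseline imbalance:
- Discharge: raw 0.85/0.72/0.56 SD, adjusted 0.70/0.64/0.53 SD, about 18/12/6% narrower.
- Average of the two later visits: raw 0.74/0.63/0.48 SD, adjusted 0.55/0.52/0.44 SD.

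A simulation of 20,000 trials agreed, except that the closed-form ANCOVA powers are about 1 to 2 points high.

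**The case against.** The strongest reply is that the right test is already planned. Group by time is a standard term of the mixed ANOVA, it is named in the plan, it is valid, and it removes baseline by subtraction. The main-effect test also keeps its type I error under randomisation, so the harm is dilution and lost power, not a false claim. All of this stands. The fault lies in which term is powered and given first place.

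Second, having no stated power does not make the interaction underpowered. Under reading 2, the only one that reproduces the plan's 80%, its power is 83% or more throughout the range shown. ANCOVA then adds only about 10/3/0 points with three visits. This also stands. Even so, the powered main effect is 8/20/31 points below discharge ANCOVA there, and the plan does not state the 1.19 or 1.59 SD that reading 2 requires.

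Third, the main effect is not always the weakest test. With three visits it slightly beats the 2-df interaction below rho of about 0.34 (reading 1) or 0.32 (reading 2). It does not beat the baseline-adjusted tests at any value shown.

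Fourth, the figures rest on one common correlation and a constant effect that the documents do not give. That is true: the sizes are conditional, though the direction of the dilution is not in doubt when baseline is a level of the time factor.

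Finally, section VI (Method of subject identification and recruitment) places an initial evaluation before consent, which differs from the order under Research design. The timing of the baseline scores is therefore unsettled. Recording them before allocation is disclosed does no harm under either order.

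**Conclusion.** The concern holds. The plan powers a group main effect that, for SODA necessarily and for pain and Quick DASH on the natural reading, averages in a visit before treatment. With a constant later difference it captures 1/2 or 2/3 of that difference and does not test greater improvement. The test that does so is secondary, has no stated power and makes no use of baseline as a covariate.

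The size depends on what f = 0.398 means and on rho, neither of which the plan states. With three visits, main-effect power is 51/43/37% if f is the post-treatment difference and 85/76/68% if it is the visit-averaged effect. The stated 80% is not shown to be wrong; it cannot be checked from the inputs given. The gain in precision from baseline adjustment depends on rho but not on f. This should be changed, but it does not make the plan invalid.

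**What to change.** - **Pain and Quick DASH:** use a linear mixed model on the discharge and 3-month values with group, visit, group by visit and baseline score. Include every randomised patient with any post-baseline value, in the allocated arm. Under missing-at-random, this keeps the discharge data of patients who miss the 3-month call.
- **SODA:** use ANCOVA at discharge with baseline SODA as covariate.
- **Main contrast:** name one in advance, either discharge or the average of the two post-baseline visits, and report group differences with 95% CIs.
- **Power:** restate it for that contrast, giving the assumed post-treatment difference, the visits used and rho.
- **Baseline timing:** record baseline scores before the patient learns the allocation. If that is not possible, state this as a limit on the covariate.

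The cost is analysis wording and standard software. No new data or visits are needed; the timing point changes only the order of steps at one visit.

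### If all three visits enter the mixed ANOVA, as its sphericity step suggests, a missed 3-month call would normally also discard that patient's discharge scores; analyse everyone assessed at each visit

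*Combined protocol and SAP*

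**What the plan says.** Under Data Analysis and Monitoring (section III), the alternative hypothesis is addressed by a "mixed design analysis of variance to test for differences between-groups and within-groups". The plan adds: "In addition we will also analyze the interaction effect between study group and time". On sphericity it says: "If Malchy's test for sphericity is significant then a Greenhouse-Geisser or Huynh-Feldt correction will be used". A repeated-measures MANOVA is optional.

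The power paragraph in the same section describes "1 between factor (group membership) and 1 within factor (repeated measures", without giving the number of repeated levels. The design "has 2 groups with 16 subjects each for a total of 32 subjects", which is also the enrolment target in section II.

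On timing, Methods and procedures, item iii, says: "Data collection are taken at baseline, and after 12 sessions of therapy at discharge". It continues: "Quick DASH and VAS scale scores and questionnaire regarding patient compliance will be completed by phone interview at 3 month follow up". The end of the Astym group's Phase III text repeats the call: "Three months after discharge from CMC, Quick DASH and VAS scale scores and questionnaire regarding patient compliance will be completed by phone interview". SODA is not part of the call.

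The text available does not say which visits enter the ANOVA. It gives no missing-data rule, analysis set or allowance for loss.

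**The concern.** With two time points sphericity holds automatically, so testing and correcting for it makes sense only with three or more. The only third time point is the phone call, and it applies only to pain and Quick DASH. Three levels for those two outcomes is therefore the natural reading.

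Under that reading, the usual implementation of a mixed ANOVA keeps only patients with all three values. Someone who finishes all 12 sessions, is assessed at discharge and then does not answer the telephone drops out of the whole analysis. In a 32-patient trial that costs power for no reason, because the discharge data exist. The optional MANOVA has the same weakness if it includes the call.

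Under the two-level reading this loss does not occur. The sphericity step is then empty and the 3-month scores have no stated analysis, which leaves room to choose one after the data are seen.

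**Working it through.** **1. The plan's own figure does not settle the number of visits.** From the power paragraph: N = 32, f = 0.398, alpha 0.05, 80% power for the between factor. For that test the noncentrality is λ = f²·N·m/(1+(m−1)ρ), with 1 and 30 df. The plan gives neither m (visits) nor ρ (correlation between visits).

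- m = 3, ρ = 0.4: 0.1584 × 32 × 3/1.8 = 8.448, power 80.3%.
- m = 2, ρ = 0.2: 0.1584 × 32 × 2/1.2 = 8.448, power 80.3%.
- ρ = 0.5: 76.1% for m = 3 and 71.1% for m = 2.

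So 80% is reachable with either two or three visits.

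**2. What deletion discards.** With 6 missed calls of 32, 96 − 6 = 90 scores per outcome are observed. Complete rows keep 26 × 3 = 78. The other 12 are 6 baseline and 6 discharge scores already collected.

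**3. Power of the planned group-by-time test.** Assumptions, none from the documents: equal correlation r between visits; no baseline difference; a difference of 2 × 0.398 = 0.796 SD at both follow-ups; everyone assessed at discharge; calls missed independently at random.

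With deletion, λ = [n₁n₀/(n₁+n₀)] × 0.796² × (2/3)/(1−r), with 2 and 2(n−2) df, n being the patients left. With 16 per arm and r = 0.4: 8 × 0.6336 × 0.6667/0.6 = 5.632, power 0.533. With losses, power is averaged over the binomial numbers left in each arm.

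Using all available visits, each patient contributes the inverse covariance matrix of the visits observed. Covariance is treated as known, with 2 and (60 minus missed calls) df. This is an approximation.

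| r | Method | 0% | 10% | 15% | 20% missed |
|---|---|---|---|---|---|
| 0.2 | deletion | .417 | .377 | .356 | .335 |
| 0.2 | all visits | .417 | .408 | .404 | .399 |
| 0.4 | deletion | .533 | .484 | .459 | .433 |
| 0.4 | all visits | .533 | .522 | .516 | .510 |
| 0.6 | deletion | .720 | .665 | .635 | .604 |
| 0.6 | all visits | .720 | .707 | .700 | .694 |

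At r = 0.4 simulation (12,000 runs each) gave .478/.461/.436 for deletion. Like for like, using all visits recovers about 4 to 8 points there.

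**4. Baseline adjustment is a separate gain.** All 32 patients, discharge only, r = 0.4:

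- Unadjusted two-visit group-by-time test: 0.796/√(2 × 0.6/8) = 2.055 on 30 df, power 51%.
- Baseline-adjusted ANCOVA: residual SD √(1 − 0.16) = 0.917, so 0.796/(0.917 × √(1/8)) = 2.457 on 29 df. Averaged over chance baseline imbalance, power is 65%.

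At r = 0.2 and 0.6 the pairs are 41% and 59%, and 68% and 76%. This gap has nothing to do with missed calls.

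**5. Bias.** With 15% of calls missed and the chance of missing depending on the discharge score (logistic slope 0.5/1.0/1.5 per SD), deletion shrinks the discharge contrast by about 0.02/0.06/0.10 SD, against a standard error of 0.33. A harsher assumption, with a 1 SD effect, about 20% missed and only control patients' calls missed according to a poor discharge score, moves the estimate from 1.00 to 0.86.

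**6. Mixed model against one ANCOVA per visit.** When only the call is missing, the mixed model's discharge contrast equals the all-patient ANCOVA. At 3 months, complete cases are simply those who answered. Under random loss the SD of the estimate is 0.365 for ANCOVA and 0.363 for the mixed model. Under the three slopes in step 5, the mean estimates are .791/.775/.769 and .796/.793/.799. The two are nearly equivalent here.

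**The case against.** The harm needs three things together: three visits in one ANOVA, software that deletes incomplete rows, and patients who attend discharge but miss the call. None is stated in the documents, and the correlations and loss rates are assumed. This stands, and it is why the point is conditional. The first rests on the sphericity step, the second is the method's normal behaviour, and nothing in the available text overrides it. The table of contents lists a section on subject withdrawal that does not appear in that text, so the claim that no rule exists goes no further than the text.

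A second objection is that a mixed model is more than the problem requires. This also stands: step 6 shows that one baseline-adjusted ANCOVA per visit does essentially as well.

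Third, single-visit contrasts are not the tests the plan names. That is true, and it is why the size is given for the planned group-by-time test. The fall at discharge in an ANCOVA after deletion (65% to 59/56/53% at r = 0.4) describes a test that is not in the plan.

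Finally, a reader might infer that the stated 80% power drops to about 71%. Taken at face value, λ = 8.383 scaled by N/32 gives 0.757/0.725/0.707 at 29/27/26 patients. But that is a different scenario: in the illustration above, the between-factor test has only 47% power before any loss. The two sets of figures must not be combined.

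**Conclusion.** The concern holds conditionally. If three visits enter the ANOVA for pain and Quick DASH, which is likely but unstated, a missed call would normally cost discharge data already in hand. For the planned group-by-time test at r = 0.4, the loss is about 5 to 10 points of power for 10 to 20% missed calls, most of it recoverable. All of this rests on the assumptions in step 3. Patients lost before discharge are outside the illustration.

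Three stronger readings are tempting and not supported. The plan does not prescribe deletion. Serious bias is not shown: it is small in most settings tried and reaches 0.14 SD only when the loss mechanism differs by arm. Nor does the two-visit reading mean that the 3-month analysis would be chosen after the data are seen; it could be, but it could also be fixed beforehand. SODA has no 3-month value and is not affected.

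**What to change.** State which visits enter each outcome's analysis. For pain and Quick DASH, replace the mixed ANOVA and sphericity step with a baseline-adjusted analysis of every randomised patient assessed at each visit, in one of two forms:

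- a likelihood-based linear mixed model with baseline, baseline-by-visit, group, visit and group-by-visit, unstructured covariance and Kenward-Roger degrees of freedom; or
- more simply, and nearly equivalent here, one ANCOVA per visit adjusted for baseline.

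Report the group contrast at discharge and at 3 months, with the sponsor naming in advance which is primary. State the missing-at-random assumption.

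The cost is a rewritten analysis paragraph and slightly more analysis work, with no extra patients or visits. The mixed model needs suitable software to be named; the plan mentions only storage software. Patients with no post-baseline visit still contribute nothing and should be counted and reported.
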